7.13.2.1. Common Adverse Events

The percentages of patients with TEAEs will be summarized using MedDRA PT for the common TEAEs (occurred in $\geq 1\%$ before rounding in any column in the table).

7.13.2.2. Deaths, Other Serious Adverse Events and Other Notable Adverse Events

The number and percentage of patients reported with an SAE during the treatment period will be summarized using MedDRA PT. A listing of SAEs will be provided.

The number and percentage of patients who permanently discontinued from study treatment due to an AE (including AEs that led to death) during the treatment period will be summarized using MedDRA PT. Events will be ordered by decreasing frequency.

7.13.3. Clinical Laboratory Evaluation

As described more fully in compound-level safety standards and in the laboratory-related PhUSE white papers (PhUSE 2013; PhUSE 2015), the clinical laboratory evaluations will be summarized as described in [Table KGAE.7.5](#). Hormone analytes are summarized/plotted similarly.

Table KGAE.7.5. Summary Tables/Listing of Clinical Laboratory Evaluations

Summaries	Population
Box plots of observed values by visit Box plots for change values by visit	Safety
Change from baseline to last observations	Safety
Scatter plots of baseline-by-maximum values and baseline-by-minimum values	Safety
Treatment-emergent abnormal high lab values (i.e., patients shifting from a normal/low maximum baseline value to a high maximum postbaseline value) or abnormal low lab values (i.e., patients shifting from normal/high minimum baseline value to a low minimum postbaseline value)	Safety
Shift tables showing the number of patients who shift from each category of maximum (minimum) baseline observation to each category of maximum (minimum) postbaseline observation. Here categories may be low, normal, or high with cut-offs defined in the compound-level safety standards.	Safety
Listing of abnormal findings for laboratory analyte measurements, including qualitative measures	Safety

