Section 2.2	Added details for secondary endpoints.	Clarification
Section 3.2	Removed text concerning prospective approval of protocol deviations.	Statement repeated text in Section 4
Section 4.1	Inclusion criterion #7: Added “non-medicated, non-prescription”. Inclusion criteria #9: “acceptable contraception” changed to “highly effective”. List of highly effective contraceptive measures revised. Inclusion criteria #10: males must use an effective barrier method of contraception for a minimum of 18 weeks following the last dose (changed from three months).	Clarification Clarification Consistency with female requirements for inclusion
Section 4.2	Exclusion criteria #3: “Eucrisa” replaced with “phosphodiesterase-4 inhibitors”. Exclusion criterion #6: add “medicated” Exclusion criteria #9: deleted reference to ACQ-5.	Globally recognized nomenclature Clarification Correction to error in protocol; ACQ-5 not utilized in this study
Section 5.1	Delete reference to placebo solution. Removed details concerning investigational product.	Correction to error in protocol; no placebo used in this study Details provided in other study-related documents
Section 5.2	Added “according to the country’s regulatory requirements”.	Clarification
Section 5.4.1	Removed details concerning administration at clinic. Added reference to Directions for Use.	Details provided in Directions for Use
Section 6.1	Added instructions on the use of systemic corticosteroids. Removed “severe” from description of infections.	Clarification Systemic antibiotics allowed for all acute infections.
Section 6.3	Clarified how topical and systemic treatments for AD may be used in the trial.	Clarification
Section 6.4	Deleted and moved text to Section 6.3.	Clarification

Protocol Section	Description of Change	Rationale
Section 7, 8.4.3 and Schedule of Visit and Procedures	Added hormone testing: estradiol in female patients and testosterone in male patients at screening, weeks 16, 32 and 52.	Safety monitoring to assess sexual maturation
Section 7.1 and 8.1.2	Added “review immunization record”.	To ensure PI reviews prior to inclusion in trial
Section 7.4, Section 7.19, Schedule of Visit and Procedures	Added PK sample collection in addition to the ADA sample.	FDA recommendation
Section 7.6	Added collection of urine sample for urinalysis	Correction for protocol consistency: listed in the Schedule of Events and Procedures

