3.2. Study Population and Number of Patients

Approximately 200 adolescent patients (≥ 12 to < 18 years, weighing ≥ 40 kg).

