4.1. Inclusion Criteria

Patients must meet all the following criteria to be eligible for this study:

1. Male or female adolescent (≥ 12 years to < 18 years and weighing ≥ 40 kg).
2. Chronic AD (according to American Academy of Dermatology Consensus Criteria) that has been present for ≥ 1 year before the screening visit (see [Appendix 2](#)).
3. Eczema Area and Severity Index (EASI) score ≥ 16 at the baseline visit.
4. Investigator Global Assessment (IGA) score ≥ 3 (scale of 0 to 4) at the baseline visit.
5. $\geq 10\%$ body surface area (BSA) of AD involvement at the baseline visit.
6. History of inadequate response to treatment with topical medications; or determination that topical treatments are otherwise medically inadvisable.
7. Apply a stable dose of non-medicated, non-prescription moisturizer at least twice daily for ≥ 7 days prior to the baseline visit.
8. Willing and able to comply with all clinic visits and study-related procedures and questionnaires.
9. For women of childbearing potential: agree to remain abstinent (refrain from heterosexual intercourse) or use a highly effective contraceptive method during the treatment period and for at least 18 weeks after the last dose of lebrikizumab.

NOTE: A woman of childbearing potential is defined as a postmenarcheal female, who has not reached a postmenopausal state (≥ 12 continuous months of amenorrhea with no identified cause other than menopause) and has not undergone surgical sterilization (removal of ovaries and/or uterus).

NOTE: The following are highly effective contraceptive methods: combined (estrogen and progestogen containing) hormonal contraception (oral, intravaginal, transdermal) associated with inhibition of ovulation, progestogen-only hormonal contraception (oral, injectable, implantable) associated with inhibition of ovulation, intrauterine device,

intrauterine hormone-releasing system, bilateral tubal occlusion, bilateral tubal ligation, vasectomized partner, or sexual abstinence. The reliability of sexual abstinence should be evaluated in relation to the duration of the clinical trial and the preferred and usual lifestyle of the patient. Periodic abstinence (e.g., calendar, ovulation, symptothermal, or postovulation methods) and withdrawal are not acceptable methods of contraception.

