12. APPENDICES

APPENDIX 1. SCHEDULE OF VISITS AND PROCEDURES

Study Procedure	Screening	Baseline	Treatment														Safety	
	Day (D): Week (W)	D1	W2 ±3d	W4 ±3d	W6 ±3d	W8 ±3d	W12 ±3d	W16 ±3d	W20 ±5d	W24 ±5d	W28 ±5d	W32 ±5d	W36 ±5d	W40 ±5d	W44 ±5d	W48 ±5d	W52/ET ±5d	12W Post ±5d
Visit Window	1	2	3	4	5	6	7	8	9	10	11	12	13	14	15	16	17	18
Visit Number	1	2	3	4	5	6	7	8	9	10	11	12	13	14	15	16	17	18
Informed Consent/Assent	X																	
Inclusion/Exclusion, Med Hx, Demographics	X	X																
Review Immunization Record	X																	
Safety																		
Vital Signs	X	X	X	X	X	X	X	X	X	X	X	X	X	X	X	X	X	X
Physical Exam, Weight/Height	X							X				X					X	
HIV, Hepatitis	X																	
Hematology, Chemistry, Urinalysis	X					X		X				X					X	
Pregnancy Test	Serum	urine		urine		urine	urine	urine	urine	urine	urine	urine	urine	urine	urine	urine	urine	
Hormone Testing ¹	X							X				X					X	
Adverse Events			X	X	X	X	X	X	X	X	X	X	X	X	X	X	X	X
Concomitant Meds & Procedures	X	X	X	X	X	X	X	X	X	X	X	X	X	X	X	X	X	X
Efficacy and Patient Reported Outcomes																		
IGA, BSA, EASI	X	X		X		X		X				X					X	
DLQI/CDLQI ²		X						X				X					X	
PROMIS Anxiety & Depression ²		X						X				X					X	
Pharmacokinetics (PK) and Immunogenicity (ADA)																		
Pre-dose PK		X		X				X				X					X	X
Pre-dose ADA ³		X		X				X				X					X	X
Study Drug																		
Administer Study Drug		X	X	X	X	X	X	X	X	X	X	X	X	X	X	X	X	
Instruction on Self-Administration						X												
Dispense Drug for At-Home Injection						X	X	X	X	X	X	X	X	X	X	X		

¹ Collect estradiol for females only. Collect testosterone for males only ² Patient reported outcome and quality of life measures should all be completed prior to other study assessments; ³ nAB testing conducted for positive treatment-emergent ADA responses. Additional immunogenicity sample collected for any patient experiencing a hypersensitivity reaction during study.

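### The planned hormone summaries take no account of age or hormonal-contraceptive use, so pooled changes are hard to read for sexual maturation

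*SAP*

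**What the plan says.** **Purpose.** The summary of changes for Protocol Amendment 1 records the addition of estradiol for females and testosterone for males at four time points, with the rationale "Safety monitoring to assess sexual maturation". The testing stands in the current text (Protocol Section 7, Section 8.4.3 and Appendix 1). The stated purpose appears only in the amendment summary.

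**Analysis.** After Table KGAE.7.5 is introduced for routine laboratory tests, SAP Section 7.13.3 says: "Hormone analytes are summarized/plotted similarly". The table, on the whole safety population, consists of box plots of values and changes, change to last observation, scatter plots of baseline against extreme values, treatment-emergent high and low, shift tables, and a listing of abnormal findings. The shift cut-offs are left to the compound-level safety standards.

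**Population.** Protocol Section 3.2 plans "Approximately 200 adolescent patients" aged 12 to under 18, in one arm. Protocol Section 4.1 accepts "combined (estrogen and progestogen containing) hormonal contraception" among the permitted methods.

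**Splits.** Efficacy subgroups are region and weight (SAP Section 7.14.1). Safety subgroups are left to the integrated safety analysis (SAP Section 7.14.2). By contrast, SAP Section 7.13.4.1 standardises weight, height and BMI for age and sex against CDC growth data.

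**The concern.** Hormone levels are informative about maturation only relative to what is expected at a given age. Over 52 weeks a 12-year-old should normally show a rise and a 17-year-old little change. A display that pools them shows an average whose size depends on the age mix, and there is no control arm to show what that average would have been without the drug.

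Estradiol has a second problem. A female who takes or starts estrogen-containing contraception can have a measured value that says little about her maturation, and the SAP has no rule to flag or separate such patients.

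What is at stake is a safety question that the sponsor raised in adolescents. Protocol Section 8.4.1 and Appendix 1 name no pubertal staging, so these two analytes are the only maturation-specific measures named. The SAP already accepts the principle of an age reference for growth and does not carry it over to hormones.

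**Working it through.** The plan gives no figure to reproduce. The sample-size rationale is redacted, and SAP Section 7.1.2 rules out inferential testing. The check therefore reads the displays one by one and then illustrates the size of the effect under stated assumptions.

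**1. What each display can show**

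- *Sex.* Appendix 1 of the protocol says "Collect estradiol for females only. Collect testosterone for males only". The sexes are therefore not mixed within an analyte.
- *Box plots and change to last observation.* These pool ages 12 to under 18 with no age reference. This is inferred from the absence of any stated split.
- *Scatter plots.* These show each patient against his or her own baseline, so a low baseline with no rise stays visible. They do not show whether a rise was expected at that age.
- *Treatment-emergent low.* This requires a move from normal or high to low. Slowed maturation is a failure to rise, not a fall. It would appear only if the lower limit rises with age, and the SAP does not say whether it does.

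**2. Pooled change under assumed maturation curves**

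None of these assumptions comes from the documents:
- The hormone level, as a share of the adult level, is logistic in age.
- The mean midpoint is 12.5, 13.5 or 14.5 years, with an SD of 1 year between patients.
- The scale is 0.5 or 0.8 years.
- Ages are uniform from 12 to under 18, and follow-up is one year.
- Half speed means that each patient moves half a year along the curve.

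| Quantity (share of adult level) | Normal | Half speed |
|---|---|---|
| Pooled mean change | +0.083 to +0.154 | +0.046 to +0.079 |
| Mean change, age 12 to under 13 | +0.155 to +0.270 | +0.063 to +0.144 |
| Mean change, age 17 to under 18 | 0.000 to +0.031 | 0.000 to +0.019 |
| Normal-to-low shift, one fixed limit at half the adult level | 0% | 0% |

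Both pooled results are rises. The lowest normal value (0.083) and the highest half-speed value (0.079) differ by 0.004, which is below the standard error of 0.010 to 0.016 at 100 patients per sex. A pooled rise of about 0.08 fits either state, depending on the assumed curve. Measured against the age-expected change, normal maturation gives 0 and half speed gives −0.035 to −0.075. The 0% shifts follow from a fixed limit and a curve that never falls, so they say nothing about age-specific limits.

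**3. Contraception**

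Assume that a share c of females start hormonal contraception on study and that estradiol falls by a share s of the adult level. The pooled mean then moves by −c × s:
- c = 0.05, s = 0.5: −0.025
- c = 0.20, s = 0.9: −0.18

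This range spans and exceeds the −0.035 to −0.075 for half-speed maturation. The documents give neither c nor s.

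**4. Gain from age bands**

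Suppose the younger half normally rises by Δ, the older half does not change, and maturation in the younger half is blunted by 30%.
- Pooled shift: 0.5 × 0.30Δ = 0.15Δ. Shift in the younger band: 0.30Δ.
- Stratum size: 200 / (2 sexes × 2 bands) = 50, if evenly split.
- Signal over standard error, with equal SD σ: pooled 0.15Δ / (σ/√100) = 1.5Δ/σ; younger band 0.30Δ / (σ/√50) = 2.1Δ/σ.
- Ratio: 2.1 / 1.5 = 1.4.

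Single-year strata would hold about 200 / 12 = 17 patients per sex, which is too few to be useful.

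**The case against.** The strongest reply is that a reader might infer that the planned analysis cannot answer the maturation question at all, and can neither show nor exclude an effect. The documents do not support that.

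- The low/normal/high cut-offs are in standards outside the SAP. Protocol Section 9.8 refers to normal ranges and Section 8.4.3 to a central laboratory, so the limits may already be specific to age and sex.
- Scatter plots, the listing of abnormal findings (SAP Section 7.13.3) and by-patient laboratory listings (Protocol Section 9.8) allow case review. Medications are recorded, so contraceptive users can be found.
- Sexual maturation is not an objective or endpoint. Its only source is an amendment rationale, and the study is descriptive.
- Safety subgroups are deliberately placed in the integrated analysis.
- A reader might also conclude that pooling halves the signal. That rests on an assumed zero change in older patients and ignores the smaller stratum. On the same assumptions the gain is about 1.4-fold, with no Δ or σ available.
- Age bands alone give no expected value. A band that rises by 0.7Δ can be called blunted only if Δ is known.

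Most of this stands and limits the claim. It does not rescue the box plots and mean changes, which have no age reference whatever the standards contain. Age-specific limits would not remove contraceptive effects from estradiol. Nothing supplied commits the integrated analysis to splitting hormones by age among adolescents or by contraceptive use.

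**Conclusion.** The point holds in limited form. As specified, the hormone box plots, changes to last observation and scatter plots do not account for age or hormonal-contraceptive use. In a single arm aged 12 to under 18, they are hard to interpret for the purpose given in the amendment. For the treatment-emergent and shift tables the age problem is an open question, not a finding.

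The size of the loss cannot be computed from the documents. The curves, the contraceptive shares and the 0.15Δ against 0.30Δ comparison are illustrations that rest on assumed values. They show that the two distortions can be as large as the effect of interest, not that they will be. Pooling is inferred from silence in the SAP. This is an inexpensive improvement to a secondary safety display and does not affect the primary endpoint.

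**What to change.** In SAP Section 7.13.3, replace the single sentence on hormones with three statements:

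1. Testosterone (males) and estradiol (females) are presented by baseline age band, for example 12 to 14 and 15 to 17 completed years.
2. Females with recorded hormonal-contraceptive use, identified from the concomitant-medication records, are shown separately from non-users.
3. Low, normal and high categories use age- and sex-specific reference ranges, so that a failure to rise is judged against an age-expected level. If the compound-level standards already do this, say so.

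The third statement is needed with the first, because bands alone supply no expected value.

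The cost is SAP wording and additional table rows from data already collected. The downside is smaller cells: about 50 per sex-by-age stratum under an even split, and fewer where females are also divided by contraceptive use. With 100 females and an assumed 5% to 20% using hormonal contraception, the user group would be 5 to 20 patients, so it may be better shown without a further age split.

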7.1. Screening Visit (Day -30 to -7)

The purpose of the screening visit/period is to ensure that appropriate patients are entered into the study and that they remain stable during the pre-treatment period.

- Obtain written informed consent/assent prior to performing any study procedures
- Review Inclusion/Exclusion Criteria
- Complete medical history/review of systems
- Collect demographic information
- Measure vital signs
- Review immunization record
- Perform a complete physical examination, including height and weight
- Collect concomitant medication and procedure/therapy information
- Complete the following assessments: Investigator's Global Assessment (IGA), Body Surface Area (BSA), and Eczema Area and Severity Index (EASI)
- Draw blood samples for laboratory tests, including serum pregnancy
- Draw blood sample for hormone testing

- Collect urine sample for urinalysis
- Instruct the patient to apply a moisturizer at least twice daily

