7.2. Baseline Visit (Day 1) Period

- Administer the DLQI/CDLQI and PROMIS anxiety and depression measures
- Update medical history/review of systems and concomitant medication and procedure/therapy information
- Complete the following assessments: IGA, BSA, and EASI
- Measure vital signs
- Draw a pre-dose blood sample for PK and anti-drug antibody (ADA) testing
- Conduct urine pregnancy test (WOCBP only)
- Re-assess and confirm patient eligibility (Inclusion/Exclusion criteria)
- Enroll the patient and administer study drug

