9.8. Other Safety Data

Laboratory data will be presented in a by-patient listing. Any clinically significant laboratory abnormalities will be captured as AEs. Changes from Baseline in safety laboratory values will be summarized by treatment group at each follow-up evaluation during the treatment period using descriptive statistics or frequency tables as applicable. Tables and listings will be in SAS format. Additionally, changes from Baseline in safety laboratory values will be summarized using shift tables according to normal ranges.

Vital signs will be presented as absolute values and changes from Baseline using descriptive statistics.

Medical histories will be coded using the MedDRA dictionary and presented in a by-patient listing. Concomitant medications will be coded using the World Health Organization drug dictionary. Concomitant medications will be summarized by treatment, drug class, and preferred term. Physical examination data will be presented in a by-patient listing. Growth monitoring of adolescents will be summarized.

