7.1.2. General Considerations for Analyses

Data will be summarized using descriptive statistics. No inferential testing will be performed. Categorical variables will be tabulated with frequencies and percentages. Continuous variables will be tabulated with mean, median, standard deviation, and range (minimum and maximum).

Baseline will be defined as the last available value before the first injection for efficacy and health outcome analyses. In most cases, this will be the measure recorded at the baseline visit (Day 1). If the patient does not take any injection, the last available value on or prior to treatment assignment date will be used. Change from baseline will be calculated as the visit value of interest minus the baseline value.

For the safety analyses, the following baselines will be used. For safety analyses using a baseline period, the baseline period is defined as the time from the screening visit to the date/time of the first injection

- TEAEs: baseline will be all results recorded during the baseline period.
- Treatment-emergent abnormal laboratory and vital signs results: baseline will be all results recorded during the baseline period.
- Change from baseline to last postbaseline observation or to each scheduled postbaseline visit for laboratory and vital signs results: baseline will be the last scheduled nonmissing assessment recorded during the baseline period.

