7.13.6.2. Eosinophilia and Eosinophil-Related Disorders

In addition to the standard laboratory summaries (Section 7.13.3), eosinophilia and eosinophil-related AEs will be summarized. Details regarding eosinophil-related PTs are in the compound-level safety standards.

Table KGAE.7.9. Summary Tables Related to Eosinophilia and Eosinophil-Related Adverse Events

Summaries	Population
Shift table summarizing the number and percentage of participants within each maximum baseline category versus each maximum postbaseline category	Safety
Summary of eosinophil-related TEAE by PT	Safety

Abbreviations: AE = adverse event; PT = Preferred Term; TEAE = treatment-emergent adverse event.

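### The laboratory shift tables compare one baseline value with the extreme of up to four later values, so with no control arm they are expected to show more shifts to abnormal than back even without a drug effect

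*SAP*

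**What the plan says.** SAP 7.13.3, Table KGAE.7.5, defines treatment-emergent high laboratory values by "patients shifting from a normal/low maximum baseline value to a high maximum postbaseline value" and treatment-emergent low values by the mirror rule on minima. The next row of the table plans "Shift tables showing the number of patients who shift from each category of maximum (minimum) baseline observation" to each category of the postbaseline extreme. Hormones are to be handled in the same way. SAP 7.13.6.2, Table KGAE.7.9, plans for eosinophils a "Shift table summarizing the number and percentage of participants within each maximum baseline category versus each maximum postbaseline category".

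SAP 7.1.2 fixes the baseline side: "Treatment-emergent abnormal laboratory and vital signs results: baseline will be all results recorded during the baseline period", where "the baseline period is defined as the time from the screening visit to the date/time of the first injection".

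The protocol determines how many values fall on each side. At screening (Protocol 7.1) the site is to "Draw blood samples for laboratory tests, including serum pregnancy". On Day 1 (Protocol 7.2) the only blood draw is to "Draw a pre-dose blood sample for PK and anti-drug antibody (ADA) testing". Appendix 1 agrees: hematology, chemistry and urinalysis are marked at screening and then at Weeks 8, 16, 32 and 52/early termination. Hormones are marked at screening and Weeks 16, 32 and 52.

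Table KGAE.7.5 also plans box plots by visit, change to the last observation and a listing of abnormal findings. Protocol 9.8 says that "changes from Baseline in safety laboratory values will be summarized using shift tables according to normal ranges" and does not mention maxima or minima.

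**The concern.** The two sides of the comparison do not hold the same number of values. The extreme of several readings lies outside a limit more often than one reading from the same patient does, so the rule leans towards shifts to abnormal whatever the drug does. In a randomised trial with equal follow-up, a control arm would carry the same lean and the comparison between arms would largely remove it. This study has a single arm (SAP 6.3), and the SAP states no expected background shift rate.

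At stake is how the categorical laboratory tables of a safety study are read. Eosinophils are the likeliest place for a misreading. They are a named special safety topic, and Protocol 1.3.1.1 reports that in an earlier trial eosinophil-associated adverse events occurred only in lebrikizumab-treated patients (3.2%). An excess of upward over downward shifts in Table KGAE.7.9 would look like confirmation, although part or all of it could come from the unequal counts.

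**Working it through.** The documents give no expected shift count, so there is no planned figure to reproduce.

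**Inputs from the documents.** About 200 patients (SAP 6.1); one scheduled baseline value; *k* = 4 scheduled postbaseline values for hematology, chemistry and urinalysis, and *k* = 3 for hormones (Protocol 7 and Appendix 1).

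**Assumed inputs.** *p*, the chance that one reading is above the upper limit, is 2.5% (range tried 1% to 10%). *ρ*, the within-patient correlation, is 0.5 to 0.9 (also tried at 0). The analyte is stable, there is no drug effect, and every patient has all *k* values.

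**Formulas.** Let *q* be the chance that one reading of a given patient is not high. Averaging over patients (E):

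- not high to high: E[*q*(1 − *q*^*k*)]
- high to not high: E[(1 − *q*)*q*^*k*]
- net: E[*q* − *q*^*k*], which is positive whenever *k* > 1 and readings vary within a patient, and zero when *k* = 1

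**Check by hand, *ρ* = 0, *k* = 4.** Here *q* = 0.975 and *q*⁴ = 0.9037. Up: 200 × 0.975 × 0.0963 = 18.8. Down: 200 × 0.025 × 0.9037 = 4.5. Net: 14.3 patients.

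**Correlated readings.** Each value is a patient effect plus noise, both normal, solved by numerical quadrature. Expected patients out of 200 at *p* = 2.5%:

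| *ρ* | *k* = 4, up / down | *k* = 3 (hormones), up / down | one value each side, up / down |
|---|---|---|---|
| 0.5 | 13.3 / 2.7 | 10.6 / 3.0 | 4.1 / 4.1 |
| 0.7 | 9.8 / 1.8 | 8.0 / 2.1 | 3.3 / 3.3 |
| 0.9 | 5.2 / 0.8 | 4.4 / 1.0 | 2.0 / 2.0 |

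A simulation of 2 million patients at *ρ* = 0.5 gave 13.2 up and 2.7 down for *k* = 4, and 4.0 and 4.1 for the last value alone.

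**Sensitivity (*k* = 4, *ρ* = 0.5).** The net excess is 4.7 patients at *p* = 1%, 10.6 at 2.5%, 18.8 at 5% and 31.8 at 10%. If 10% or 30% of patients had only one postbaseline value, the 10.6 would fall to 9.5 or 7.4. Shifts to low on the minimum behave symmetrically.

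**Selection at screening.** Exclusion criterion 15 removes patients whose screening laboratory results the investigator judges clinically significant. If that removed half of the high screening values (an assumption), the one-value-each-side comparison at *ρ* = 0.5 would no longer balance: about 4.1 up against 4.1 ÷ 2 ≈ 2.1 down.

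**The case against.** The strongest reply is that extreme-value displays are a recognised way to find outliers and that the SAP does not rest on them alone. It plans no tests and no formal comparison of upward with downward shifts, and the primary endpoint is discontinuation due to adverse events. Box plots by visit and change to the last observation do not use extremes, clinically significant abnormalities are recorded as adverse events, and Protocol 9.8 foresees frequency tables at each follow-up evaluation where applicable. The SAP also refers to compound-level safety standards for cut-offs and fuller descriptions. Those standards are not among the documents and might contain further tables or footnotes.

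Much of this stands, and it limits the point. A reader might infer that a true laboratory signal could not be told from the artefact. The documents do not support that: a sustained change would appear in the by-visit displays. What remains is that no categorical table listed in Table KGAE.7.5 or KGAE.7.9 sets one value against one value, so no listed table gives an even-handed count of patients becoming abnormal and returning to normal. The absence of testing does not help, because counts labelled treatment-emergent are read as drug-associated without a p-value.

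Two further extensions are tempting and should not be made. Vital signs have more readings after baseline than before, but SAP 7.13.4 pairs a specified limit with a required change, so these figures do not carry over. Nor can the per-analyte rates be compounded into a share of patients with any abnormal analyte. Related analytes such as hemoglobin and hematocrit are not independent, and Table KGAE.7.5 lists no such table.

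**Conclusion.** The point holds for the extreme-value laboratory tables, including eosinophils and hormones. The direction follows from the schedule and the rule for any stable analyte with two or more postbaseline values. The size rests on assumed inputs: with 2.5% of readings high and a correlation of 0.5 to 0.9, about 5 to 13 patients in 200 shift up against 1 to 3 down, a ratio of roughly five or six to one. For hormones it is about 4 to 11 against 1 to 3.

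A reader might take this as a certainty that the tables will show net worsening. It is an expectation under stability. A real downward trend over 52 weeks in adolescents could mask it, and an upward trend would add to it. Early terminators may have fewer than four values, which shrinks the excess. An unscheduled repeat enters whichever side it falls on. Selection at screening works in the other direction and tends to enlarge the imbalance.

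**What to change.** In Tables KGAE.7.5 and KGAE.7.9, add two-way shift tables from the last scheduled baseline value to the value at each scheduled visit: Weeks 8, 16, 32 and 52, or Weeks 16, 32 and 52 for hormones. State that change in abnormality is interpreted from these. SAP 7.1.2 already defines the last-scheduled baseline for change analyses, and Protocol 9.8 already allows frequency tables by evaluation.

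Keep the maximum and minimum tables for detecting outliers. Add a footnote giving the scheduled number of values on each side and saying that more shifts to abnormal than back are expected from this alone. Add a second note, to the by-visit tables, that excluding clinically significant screening results can leave some upward imbalance there through regression to the mean.

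The cost is SAP wording and a few extra tables from data already collected, as an addition to the compound-level standard displays. By-visit shifts can miss a transient abnormality, which is the reason to keep the extreme-value tables beside them.
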